- Baseline Survey: This survey collects demographic information and asks participants about their medical visits, knowledge on their rheumatic disease as related to pregnancy and risk, as well as their experiences with birth control, pregnancy, and healthcare services for women.

G2c. T1: Intervention

For telemedicine participants, T1 will be completed prior to their remote clinic visit.

Participants randomized at enrollment to the intervention arm will access the MyVoice intervention tool. Those randomized to the control arm will access the American College of Rheumatology online pamphlet. This access will be given prior to their clinic visit. Participants randomized to the intervention arm will have approximately 20 minutes to navigate through the MyVoice decision tool.

For telemedicine participants, patients who have not completed their forms will receive one text (using Google Voice) or email every day to remind them to complete the forms prior to their rheumatology appointment. The final reminder will occur 3 hours before their clinic visit. If forms are still not completed before their clinic visit patients will be contacted to inform them that they are withdrawn from the study. If these patients have an additional rheumatology appointment within the recruitment period and are still interested in participating, they will be given the option to reschedule their study visit and will not be considered withdrawn.

Patients randomized to the intervention arm will have the option to print out a summary of the questions they have asked and decisions they have made using the tool (i.e., the MyVoice summary sheet) to bring to their appointment if they have access to a printer.

G2d. T2: Up to 48 Hours Post-Intervention

For telemedicine participants, T2 forms will be completed up to 48 hours post-intervention after their rheumatology visit.

The following forms are to be completed at T2:

- Exit Survey: This survey asks participants questions regarding acceptability and implementation measures for the MyVoice tool.

After completion of the exit survey, women will also engage the research coordinator in a post-visit phone interview to discuss their perceptions and reactions to the MyVoice tool and their experience using it. This interview will take approximately 20 minutes.

Ideally, the exit survey and interview will be completed immediately after the patient leaves her rheumatologist visit. However, if participants are unable to complete the study activities at that time, research coordinators will schedule a time to complete them over the phone between 24-48 hours after the visit.

Research coordinators will collect the following PHI from electronic health records of participants within 24 hours of their rheumatology visit, and again 90 days later at T4:

- Orders for pregnancy tests (urine, serum)
- Orders for emergency contraception
- Billing code for family planning or contraception counseling
- Order for non-emergency contraception method
- Order/Referral for obstetrics-gynecology or maternal-fetal medicine consultation
- Order/Referral for PCP consultation for family planning indication
- Prescription for prenatal vitamin
- Change from fetotoxic/teratogenic disease-modifying anti-rheumatic drug or small molecule medication to a pregnancy-compatible anti-rheumatic drug
- Documentation of pregnancy

G2e. T3: 2 Weeks Post-Recruitment Completion (Providers)

T3 is a time point only relevant to rheumatology providers. No action is needed from participants at T3.

The following forms will be completed at T3:

- Provider Survey: This survey will be given to rheumatology providers with one or more patients enrolled in the research study. This survey asks providers about their

experience with the study as well as information related to encounters with patients enrolled in the study.

Providers will be emailed this survey to complete through a REDCap link. Emails with the REDCap link to the survey will be sent out 2 weeks after our final participant completes their T2 survey. Providers will **NOT** be informed of which of their patients participated in the study. Study personnel will follow up with providers once a week via email to complete the survey a maximum of three times.

G2f. T4: 3 Months Post-Intervention

T4 will begin for participants 3 months post-intervention.

The following forms will be completed at T4:

- 3 Month Survey: This survey asks participants about any potential pregnancies post-intervention, their current birth control habits, and their knowledge on pregnancy risks in the context of rheumatic disease.

Participants will be emailed this survey via a REDCap link (as described in REDCap instructions section). Prior to emailing, study personnel will call participants to remind them of their upcoming survey. Study personnel will follow up with participants once a week via email to complete the survey for a maximum of three times.

Participants will also complete a follow-up interview at the T4 time point. Research coordinators will reach out to participants 3 months post-intervention to schedule the interview. Coordinators will reach out to schedule interview once a week via email and phone to complete the survey for a maximum of three times.

Research coordinators will collect the following PHI from electronic health records at T4:

- Orders for pregnancy tests (urine, serum)
- Orders for emergency contraception
- Billing code for family planning or contraception counseling
- Order for non-emergency contraception method
- Order/Referral for obstetrics-gynecology or maternal-fetal medicine consultation
- Order/Referral for PCP consultation for family planning indication
- Prescription for prenatal vitamin
- Change from fetotoxic/teratogenic disease-modifying anti-rheumatic drug or small molecule medication to a pregnancy-compatible anti-rheumatic drug
- Documentation of pregnancy

G3. Clinic Participants

Clinic participants will be asked to arrive to their rheumatology clinic visits 1 hour early to complete required study activities. Research coordinators will meet with participants in an available space in the clinic. If space is not available, study activities will be completed outside (weather permitting) or in a neutral space inside.

G3a. Consent

Consent will occur prior to performing any of the research interventions/interactions and before the participant goes to their clinic appointment. At consent, a research coordinator will walk through the informed consent document with participants and answer any questions that arise. If the participant agrees to participate, both the participant and the research coordinator will sign the informed consent document. They will also sign a HIPAA authorization allowing study personnel to access their medical records.

G3b. T0: Baseline

The following forms are to be completed at T0:

- Baseline Survey: This survey collects demographic information and asks participants about their medical visits, knowledge on their diseases as related to pregnancy, as well as their experiences with birth control, pregnancy, and healthcare services for women.

G3c. T1: Intervention

For clinic participants, T1 will be completed prior to their clinic visit.

Participants randomized at enrollment to the intervention arm will be administered MyVoice on a computer tablet provided by the research coordinator. Those randomized to the control arm will be given a paper version of the American College of Rheumatology online pamphlet. Participants randomized to the intervention arm will have approximately 20 minutes to navigate through the MyVoice decision tool.

To comply with social distancing in the clinic, the location in which the patients complete the survey will be delineated prior to their appointment. We will work with UPMC clinic management to see if there is an available room in which the patients can complete the surveys and tool or assess if they should be met at their cars and given the study materials.

Patients randomized to the intervention arm will be given a copy of the summary sheet (printed by a research coordinator) with questions they have asked and decisions they have made using the tool to bring to their appointment.

G3d. T2: Up to 48 Hours Post-Intervention

For clinic participants, T2 forms will be completed up to 48 hours post-intervention after their rheumatology visit. Ideally, clinic patients will complete this immediately after their rheumatology visit.

The following forms are to be completed at T2:

- Exit Survey: This survey asks participants questions regarding acceptability and implementation measures for the MyVoice tool.

After completion of the exit survey, women will also engage the research coordinator in a post-visit interview to discuss their perceptions and reactions to the MyVoice tool and their experience using it. This interview will take approximately 20 minutes and will be completed either in person in an open space at the clinic or via phone, depending on the participants' preference.

Ideally, the exit survey and interview will be completed immediately after the patient leaves her rheumatologist visit. However, if participants are unable to complete the study activities at that time, research coordinators will schedule a time to complete them over the phone between 24-48 hours after the visit.

Research coordinators will collect the following PHI from electronic health records of participants within 24 hours of their rheumatology visit, and again 90 days later at T4:

- Orders for pregnancy tests (urine, serum)
- Orders for emergency contraception
- Billing code for family planning or contraception counseling
- Order for non-emergency contraception method
- Order/Referral for obstetrics-gynecology or maternal-fetal medicine consultation
- Order/Referral for PCP consultation for family planning indication
- Prescription for prenatal vitamin
- Change from fetotoxic/teratogenic disease-modifying anti-rheumatic drug or small molecule medication to a pregnancy-compatible anti-rheumatic drug
- Documentation of pregnancy

G3e. T3: 2 Weeks Post-Recruitment Completion (Providers)

T3 is a time point only relevant to rheumatology providers. No action is needed from participants at T3.

The following forms will be completed at T3:

- Provider Survey: This survey will be given to rheumatology providers with one or more patients enrolled in the research study. This survey asks providers about their experience with the study as well as information related to encounters with patients enrolled in the study.

Providers will be emailed this survey to complete through a REDCap link. Emails with the REDCap link to the survey will be sent out 2 weeks after our final participant completes their T2 survey. Providers will **NOT** be informed of which of their patients participated in the study. Study personnel will follow up with providers once a week via email to complete the survey a maximum of three times.

G3f. T4: 3 Months Post-Intervention

T4 will begin for participants 3 months post-intervention.

The following forms will be completed at T4:

- 3 Month Survey: This survey asks participants about any potential pregnancies post-intervention, their current birth control habits, and their knowledge on pregnancy risks in the context of rheumatic disease.

Participants will be emailed this survey via a REDCap link (as described in REDCap instructions section). Prior to emailing, study personnel will call participants to remind them of their upcoming survey. Study personnel will follow up with participants once a week via email and phone to complete the survey for a maximum of three times.

Participants will also complete a follow-up interview at the T4 time point. Research coordinators will reach out to participants 3 months post-intervention to schedule the interview. Coordinators will reach out to schedule interview once a week via email and phone to complete the survey for a maximum of three times.

Research coordinators will collect the following PHI from electronic health records at T4:

- Orders for pregnancy tests (urine, serum)
- Orders for emergency contraception
- Billing code for family planning or contraception counseling
- Order for non-emergency contraception method

- Order/Referral for obstetrics-gynecology or maternal-fetal medicine consultation
- Order/Referral for PCP consultation for family planning indication
- Prescription for prenatal vitamin
- Change from fetotoxic/teratogenic disease-modifying anti-rheumatic drug or small molecule medication to a pregnancy-compatible anti-rheumatic drug
- Documentation of pregnancy

G4. Troubleshooting

For telemedicine and clinic participants, T0 (baseline) is completed before their scheduled rheumatology appointments. While participants will be asked to arrive one hour early to their appointments to complete study activities, we suspect that everything can be completed in 45 minutes. If participants arrive more than 20 minutes late to their scheduled study appointment, research coordinators will inform them that they cannot complete the first part of the study that day. If the participant has another upcoming rheumatology appointment within one month, they can be rescheduled. If they do not, they will be withdrawn from participation.

J. Payment Protocol

H1. Full Study Completion

Participants who complete all study activities in time points T0-T3 will receive \$40 payable by a university-issued payment card (Vincent). This payment card will be loaded and issued to the participant by the research coordinator and will be reloaded with additional funds if and when the participant completes follow up visits. For telemedicine participants, Vincent cards will be mailed to them. Participants will be asked to contact the study team upon receipt of their card for the study team to activate it. Clinic participants will be given their loaded Vincent cards at the time of their study visits. Participants will be instructed to keep their Vincent cards until the completion of the study (3 months post-intervention).

Participants who complete the study remotely (telemedicine) will receive an additional \$10 on their payment card to compensate for data usage and cell phone minutes, regardless of how much of the study they complete. Those who complete the study in-person (clinic) will receive a parking voucher, worth \$8-10.

Participants who complete the interview at T4 (3 months post-intervention) will receive an additional \$20 on their Vincent cards.

H2. Partial Study Completion

Because the study is voluntary and participants have the option to withdraw at any time, there is potential for partial payment depending on how much of the study is completed. Partial payment guidelines are listed below, described as how much a participant would receive if withdrawing after completing the listed study activity.

- Consent: \$0
- Baseline survey/Intervention (MyVoice/pamphlet): \$5

Telemedicine participants that only complete a portion of the study will still be compensated an additional \$10 for data usage and cell phone minutes, regardless of how much of the study they complete.

I. Communication Protocol

Participants will be asked how they would prefer to be contacted for study reminders and communication (call, email, text, or any combination of these options).

For those who request text message communication or reminders, texts will be sent by the study team using Google Voice to remind participants about upcoming appointments. Google Voice generates a unique [contact]) and allows research staff to communicate with participants via phone and text anonymously without needing to provide personal phone numbers to participants.

Phone numbers for texting are also included on recruitment materials. Participants will be able to contact the study team via Google Voice texting with study related questions. Messages and contact information will not be stored on or downloaded to any devices. Research staff will delete text message chains on a regular monthly basis. The content of the messaging is limited to appointment reminder and study related information questions.

A study specific email address was created for communication with participants during recruitment and for scheduling/appointment reminder purposes. This study email address is: [contact].

J. Protocol for Withdrawal/Lost to Follow Up

J1. Withdrawal

Participants are able to withdraw from study participation at any time for any reason. To withdraw, a participant must either provide verbal or written notification that they want to withdraw from the study and discontinue any ongoing study activities. Any information and data collected prior to withdrawal will be retained and can be used for research-related purposes, unless specified by participant at withdrawal.

At the time of participant withdrawal, research coordinators will load a Vincent card for the withdrawn participant with the appropriate payment amount as delineated in the Payment Protocol section. Coordinators will then complete the Withdrawal Form in REDCap.

J2. Lost to Follow Up

Participants will be deemed lost to follow up if they participate in the intervention but are unable to be reached for future study activities (time point T2). To clarify, if participants do not complete the exit survey/interview after their rheumatology appointment, research coordinators will attempt to schedule study activities 24-48 hours after their visits (described in Study Procedures section). If study staff is unable to reach them to schedule and they do not hear from the participant to complete the study activities, participants will then be considered lost to follow up. Coordinators will then complete a Lost to Follow Up form in REDCap.

Note: Because T4 study activities are supplemental to the main study data, participants that cannot be reached to complete the final 3-month survey will not be considered lost to follow up.

K. SAFETY ASSESSMENTS

1. Study oversight is being conducted by an internally-appointed Safety Officer, [name], Assistant Professor in the Department of Obstetrics, Gynecology & Reproductive Sciences at the University of Pittsburgh.

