T2: Exit Survey

- Acceptability and implementation measures for the MyVoice tool
- Reproductive knowledge (ReproKnow)
- Self-efficacy (Perceived Efficacy in Patient-Provider Interactions [PEPPI])
- Decision Conflict Scale (Low Literacy version)
- Interpersonal Quality of Family Planning (IQFP) Scale

T3: Provider Survey

- Providers' experiences with the study as well as information related to encounters with patients enrolled in the study

T4: 3 Month Survey

- National Survey of Family Growth Family Planning Services Question
- Self-efficacy (Perceived Efficacy in Patient-Provider Interactions [PEPPI])
- Reproductive knowledge (ReproKnow)
- London Measure of Unintended Pregnancy

D. Risk/Benefit Assessment

Known Potential Risks

- Discomfort- Study activities involve information regarding reproductive health; some individuals may be uncomfortable discussing this topic.
- Invasion of Privacy- Participants may feel uncomfortable discussing their reproductive health where other individuals may hear them.
- Breach of Confidentiality- Any possibility that de-identified information could be viewed by unauthorized parties.

Known Potential Benefits

- This pilot study will inform the procedures and practices related to a future full-scale testing of a patient-facing decision support tool for family planning. Our study team and others have demonstrated that women with rheumatic diseases do not receive adequate family planning care. We will not directly counsel patients about their particular risks, and therefore, patients will not receive a direct benefit from their participation. However, they may learn more about their family planning options in the context of their diseases.

Assessment of Potential Risks and Benefits

- Discomfort- We will minimize occurrence of discomfort by being clear about the content of the study tool and assessment measures during recruitment. All questions in study surveys and interviews will be optional, and participants will be told they can skip any question they do not wish to answer.
- Invasion of Privacy- The study will not be discussed with potential or current participants in public settings. Conversations about the study will only occur in private exam rooms or research spaces or via email or phone conversations. We will minimize risk by placing phone calls while in a private room and asking the potential participant whether they are in a private location before discussing the study.

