Then, you'd have your visit with your rheumatologist. We'd like to interview you within a week of the visit to see how the visit with your rheumatologist went, and to give you some additional

surveys. This step would probably take an additional 30 minutes or so. We'd need to be able to talk with you over the phone. Our research coordinator will also look in your chart immediately after the visit, and 90 days after your visit.

We think altogether, you might expect to spend about two hours on the study. We would compensate you with \$40 for completing the study and \$10 to go towards your use of your cell phone minutes or data.

I should mention that your rheumatologist will not be told that you are participating in the study, and all of your survey and interview content will be kept confidential.

Might you be interested in participating in the research study? If so, I have a consent form that I will send you. If you are interested, I can go over this document with you verbally and you can consent for the study now over the phone.

If No, thank the patient and hang up.

If Yes, continue with the verbal consent.

Interview Guide

Note: Consent for participation in the study will have previously been obtained.

INTRODUCTION: (OPTIONAL)

Hello. My name is XXX. I am very appreciative that you are taking the time to talk with me today. The purpose of this research study is to hear about your thoughts and opinions related to the MyVoice:RD decision aid as well as your experiences and perspectives regarding reproductive health discussions you may have had with your rheumatologist. What we learn from talking with women like you will help us improve the tool and this aspect of care for women with rheumatic diseases.

I am going to use an audio recorder to tape our conversation. Our conversation will be entirely anonymous, which means that I won't share this recording with anyone but our study team. We will not use your name or the name of anyone else you mention in this interview.

I really want to make sure that you feel comfortable sharing your experiences and opinions with me. All questions are voluntary, so you don't have to answer any that you don't want to. You can stop participating at any time. If there are any comments or thoughts that you'd like to add, I'd love to hear them.

There are no risks or benefits to participating in this interview. I expect that the interview will take around 20-30 minutes to finish.

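### The clinic exit interview may be held in an open space, contrary to the protocol's own rule that study conversations stay private

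*Combined protocol and SAP*

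**What the plan says.** Section D (Risk/Benefit Assessment) lists invasion of privacy as a known risk: "Participants may feel uncomfortable discussing their reproductive health where other individuals may hear them". Its mitigation has two parts: "The study will not be discussed with potential or current participants in public settings", and "Conversations about the study will only occur in private exam rooms or research spaces or via email or phone conversations".

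The clinic procedures are written differently. Section G3 has the coordinator meet the participant wherever the clinic has room and adds: "If space is not available, study activities will be completed outside (weather permitting) or in a neutral space inside". Section G3d says that the exit interview "will be completed either in person in an open space at the clinic or via phone", whichever the participant prefers. It also sets the preferred timing: "Ideally, the exit survey and interview will be completed immediately after the patient leaves her rheumatologist visit". If that is not possible, the exit survey and interview are done by phone 24 to 48 hours after the visit.

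Sections D4 and G3e say that study staff will not tell providers which of their patients took part.

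**The concern.** The only in-person location written for the exit interview is one that the privacy safeguard does not allow. The Interview Guide in the Appendix covers parenthood, pregnancy and birth control. It also asks whether the woman felt heard and whether her provider listened. The conversation is recorded and would ideally follow straight after she leaves that provider.

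Two things are at stake. The first is the participant's privacy: she could be overheard, and being seen in an interview could disclose to clinic staff that she is in the study. The second is the quality of the interview data. A woman who may be overheard at the clinic that treats her may say less, or say it differently. The SAP codes these interviews for whether family planning was discussed, the reasons, and the barriers and facilitators.

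**Working it through.** No formula applies and the plan gives no figure to reproduce. The check sets each spoken or written clinic activity against the settings that section D permits: private exam room, research space, email, phone.

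1. **Consent (G3a).** The coordinator goes through the document aloud and answers questions. Under G3 this may happen outdoors or in a neutral indoor space. Such a place could turn out to be private, but nothing requires it. Result: not secured.
2. **Baseline and exit surveys (F3, G3b, G3d).** In clinic these are normally self-completed on an iPad, and F3 says that answers are given confidentially. Little is spoken. Result: largely consistent with section D, even outside a private room.
3. **Exit interview in person (G3d).** The setting named is an open space at the clinic. On its ordinary reading this is neither a private exam room nor a research space. Result: contradicts section D.
4. **Exit interview by phone (G3d).** Result: consistent with section D.

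**Where the data go.**
- The SAP's qualitative analysis uses the interview transcripts, so the themes are exposed. So is the coded yes/no on whether family planning was discussed. The SAP does not say whether the reported comparison of discussion rates between arms rests on that coding or on a survey item.
- AIM, IAM and SUS are scale scores. The exit survey is the instrument described as holding the acceptability measures, so I assume that these scores come from it and not from the interview.

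**How many women.** The Results give 55 consented, 46 randomised and 40 completers (31 MyVoice + 9 control). Neither the clinic/telemedicine split nor the in-person/phone split is given. The bounds are therefore:
- consent discussion in a non-private place: 0 to 55;
- exit interview in an open space: 0 to 40, taking completers as those interviewed;
- reported interview themes, which come from MyVoice users only: 0 to 31.

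These are limits, not estimates.

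**The case against.** The strongest reply is that nobody is forced into an open space. Phone is offered at the woman's preference, every question is voluntary, and a site that uses phone satisfies both sections. That stands, and it rules out the inference that a site cannot comply with both. It does not remove the conflict, because no private in-person option is written and the preferred timing favours an interview on site.

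Open may have been meant as available, since G3 speaks of whatever space the clinic has. That is possible, but neither sense requires privacy.

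A reader might go further than the documents allow in four ways:
- **That answers were biased towards favourable ones.** No section gives a direction or size, and reticence could simply shorten answers. Unfavourable content was still reported, including distrustful relationships and rushed visits.
- **That the acceptability results or the comparison of arms are compromised.** The scale scores are self-completed. Telemedicine women are interviewed by phone, so the setting may differ by mode of participation, but G1 does not allocate by mode and no bias between arms is shown.
- **That women are asked about trust in their rheumatologist.** Trust is a theme that emerged. The scripted prompts concern feeling heard and being listened to.
- **That a promise to clinic women is broken.** The Screening Script says "I should mention that your rheumatologist will not be told that you are participating in the study", but it describes a study conducted remotely, and not being told is narrower than never finding out. Clinic intervention users also receive a printed summary to take to the appointment. Sections D4 and G3e are the firmer support, and they cover only what study staff disclose.

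**Conclusion.** The contradiction is real and can be read directly from the text: G3d permits, and G3 leaves open, settings that section D excludes as its mitigation for a risk that the protocol itself names. It is more than a clerical slip, because section D concludes that benefits outweigh risks after setting out these safeguards. It should be corrected, but it does not undermine the trial's quantitative findings.

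The effect on data is limited to a plausible loss of candour in the qualitative interviews, of unknown direction and size. This rests on three assumptions: that open space carries its ordinary meaning, that AIM, IAM and SUS were collected in the exit survey, and that at least some clinic women were interviewed in person. The documents do not confirm the last of these.

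**What to change.** Reconcile G3 and G3d with section D:
- Delete the reference to an open space at the clinic. State that the consent discussion and the exit interview take place in a private room or research space. If none is free, hold the interview by the phone option already offered, within the existing T2 window.
- Limit any outdoor or neutral-space activity to silent self-completion of surveys and the tool.
- Record the setting of each interview (private room, phone, other) and describe it when the themes are reported. Formal comparison by setting is not worthwhile, because 31 and 9 completers would split into very small cells.

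The cost is a short wording change and one data field. The small downside is that some interviews move to phone and take place later, with some women to re-contact.

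Because results are already reported, the wording change cannot alter these interviews. It applies to reuse of the procedures in the larger trial that this pilot is meant to inform. For the present trial, describe the interview settings where they can be recovered, or state the gap as a limitation.
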